## GENERAL INFORMATION:

**Title:** Adaptation of an Evidence-based Interactive Obesity Treatment Approach (iOTA) for Obesity Prevention in Early Serious Mental Illness: iOTA-eSMI

**Short Title:** iOTA-eSMI

## OBJECTIVES:

The main objectives of this study are:

### Study Aims:

- I) **Evaluate barriers and facilitators for intervention engagement, effectiveness and implementation, and identify needed adaptations of the prior iOTA for use in obesity attenuation in Early Serious Mental Illness (eSMI).** We will conduct multi-level provider, client, and caregiver focus groups and interviews within two Community Mental Health Centers (CMHC) systems – one in Missouri (MO), and one in Florida (FL) – to characterize qualitative factors relevant to intervention engagement, effectiveness and implementation within diverse care environments. Client and caregiver assessments will specifically characterize client-level determinants of intervention engagement.
- II) **Adapt the prior iOTA for use in obesity attenuation in eSMI.** Using the multi-level qualitative data collected in Aim 1, we will adapt health coach visits and SMS messaging to maximize acceptability, engagement, sustainable reach and target engagement for eSMI. Key components of the adapted intervention will be reviewed with participants from Aim 1 to identify any additional needed adaptations.
- III) **Conduct a randomized pilot and feasibility study of iOTA-eSMI in a diverse sample of adults with eSMI, comparing iOTA-eSMI to a health education control condition.** iOTA-eSMI will be piloted in a representative sample of 60 adults from MO and FL CMHCs with eSMI, randomizing participants 2:1 to 24 weeks (6 months) of iOTA-eSMI involving daily goal-specific text messaging and self-monitoring prompts, versus monthly health education control condition that includes weekly non-specific supportive text messaging. Both groups will then enter a 12-week continuation phase of text messaging only. We hypothesize favorable differences in weight change from baseline for iOTA-eSMI compared to control. Secondary analyses will assess effects on RDoC domains relevant to psychophysical skills and self-efficacy, exploring the relationship between weight change and target engagement. Feasibility, engagement and implementation challenges will be measured by i) enrollment & retention, ii) intervention acceptability, iii) text response rates, iv) visit adherence v) client expectations, vi) fidelity and vii) CMHC staff-rated acceptability, appropriateness and burden.

## BACKGROUND AND RATIONALE:

Most obesity and related complications in serious mental illness (SMI) occur with chronic treatment. Behavioral interventions to reverse obesity in chronic SMI face challenges with long-term effectiveness and/or challenges with implementation and sustainability. There are no FDA-approved pharmacotherapies for obesity in SMI, and off-label treatments have limited effectiveness and/or serious adverse event risks. Using low-cost, simple digital health approaches such as SMS messaging for increased support and accountability during lifestyle interventions has been shown to lead to increased engagement, especially among youth and young adults.

## PROCEDURES:

### AIM 1

*Aim 1* will build on our chronic SMI iOTA pilot data to determine how to best facilitate health behavior change in eSMI patients through interventions at the levels of the CMHC and the individual. Using the I-Corps discovery methods, we will conduct focus groups with CMHC administrators, physicians, nurses, case managers, clients and client family members/caregivers to identify barriers and facilitators to use of an iOTA intervention for

health behavior change and weight loss/obesity prevention in eSMI. Information gained in Aim 1 will drive the intervention adaptation process proposed in Aim 2, by helping to shape simple and actionable individual health behavior change messages, and by identifying feasible changes in the cultural, organizational, and physical CMHC environment that will help workers achieve and sustain healthy weight. Activities in Aim 1 will ensure that health messages and other intervention components are relevant and culturally appropriate.

**Study participants** will include eight focus groups of five participants each, conducted at each CMHC site, for a total of 16 focus groups. Group composition will reflect the age, racial and ethnic distribution of the population at each site.

**Inclusion criteria:** 1) focus group participants for CMHC Administrators will include individuals holding leadership roles within the CMHC structure: clinical director, medical director, nursing director, case management supervisor, clinic manager; ii) participants for CMHC prescribers will include advanced practice nurses, physician's assistants and physicians who see patients and prescribe medications within the CMHC setting; iii) participants for CMHC nursing staff will include registered nurses, licensed practical nurses, nurse health coaches and nurse managers who provide care within the CMHC setting; iv) participants for CMHC case managers will include community support workers and case managers; v) participants for CMHC clients will include individuals ages 18-45 with SMI (e.g., depression with psychotic features, bipolar disorder, schizophrenia or schizophreniform disorder) who receive case management and psychiatric and/or medical services within the CMHC setting; vi) participants for CMHC client family/caregivers will be family members or caregivers of client participants; vii) all participants are willing/able to provide written informed consent.

**Exclusion criteria:** i) not willing/able to provide written informed consent; ii) participants under age 18.

## Aim 1 Study Procedures

*I-Corps Approach to Focus Groups and Interviews:* The Innovation Corps method uses the Lean

Launchpad approach to developing hypotheses, then quickly moving to a continuous customer discovery method with the aim of translating hypotheses into facts. In this study, the process will begin with developing a list of hypotheses about the problem under study with the study team, consisting of faculty and community partners, here specifically regarding barriers or challenges to implementing an iOTA program in a CMHC environment. Then the

**Table 1: Focus Group Makeup and Questions**

Focus Group	# Groups per Site	Participants	Areas of Interest
CMHC Administrators	1	Medical Director (1), Director of Nursing (1), Clinical Director (1), Case Manager Supervisor (1), Clinic Manager (1)	1) What should the qualifications and characteristics of the health coach be? Is it reasonable for the health coach to be an existing CMHC clinical or other type of staff member? Or should it be someone else? 2) How often should health coaches meet with clients face-to-face? What should the content of the meetings be? 3) How frequent should text messages be? What should the content of the messages be? Is it helpful to have two-way texting capability?
CMHC Prescribers	1	Psychiatrists (1-2), Advanced Practice Nurses (1), Physician Assistants (1), Primary Care Physicians (1)	4) How much time could an existing staff member devote to intervention delivery? What would the optimal amount of time be for intervention effectiveness?
CMHC Case Managers	1	Case Managers (2) and Community Support Workers (2-3) from adolescent and adult teams	5) Are there age-specific modifications needed to make the intervention more feasible/acceptable to adolescents and young adults? 6) Are there modifications needed to address other social determinants of clients and caregivers? (Race/ethnicity, gender, socio-economic status, level of education?)
CMHC Nursing Staff	1	Nursing staff (1-2), nurse care managers (1-2), nurse health coaches (1)	
CMHC Clients	2 - Group composition will reflect the racial and ethnic distribution of the population at each site.	Adult clients ages 18-45 (2-3)	
CMHC Client Family/Caregivers	2 - Group composition will reflect the racial and ethnic distribution of the population at each site.	Parents (2-3), adult siblings (1) or other adult family members of client group participants (1-2)	

team identifies individuals who are representative of consumers/customers at multiple levels within the organization who can inform the questions. These are our focus group participants – administrators, clinicians (nurses, case managers, physicians), clients and caregivers. Interviews and focus groups are conversational and discovery-oriented, with the goal of testing hypotheses. Focus group composition will be monitored to balance groups with respect to age, race and gender, taking care to include outlier perspectives. Once facts about the hypotheses have been obtained, the team will review all interview and focus group data, looking for emergent themes. This allows the team to determine the “value proposition” for the customer or key stakeholder, identifying potential “pain” and “gain” areas. The team can then determine actions needed to change or adapt iOTA to best fit the CMHC environment.

**Focus Group Makeup, Preparation & Topics** Purposive sampling methods will be applied to avoid bias in focus group responses, working with community partners to ensure group composition represents a broad range of perspectives. Six focus groups will be conducted at each community site, and will consist of:

- 1) Administrators (medical director, director of nursing, director of clinical services, case manager supervisor, clinic manager)
- 2) Prescribers (psychiatrists, advance practice nurses, physician assistants, primary care physicians)
- 3) Nursing staff (nursing staff, nurse care managers, nurse health coaches)
- 4) Community clinicians (community support specialists and case managers)
- 5) Transition-age clients (18-45 years)
- 6) Client family or caregiver (parents, adult siblings or other adult family members)

Once focus group participants are identified, they will be asked to participate in one in-person or phone visit to set up health goals and related text messages. They will then participate in 1-2 weeks of iOTA text messaging so as to facilitate optimal feedback on intervention adaptations. Focus groups will be scheduled within 1 week of completing the 2-week iOTA trial. Groups will be conducted at the CMHC site during a time that is convenient for participants, and will be facilitated by a research assistant facilitator and CMHC staff member taking additional notes. Groups will be digitally recorded. Focus group areas of interest will include:

- 1) What should the qualities and characteristics of the health coach/interventionist be?
- 2) What would be the optimal workload associated with intervention delivery?
- 3) What are the optimal qualities and content of the in-person iOTA intervention component?
- 4) What are the optimal qualities and content of the text-messaging intervention component?
- 5) What age-specific intervention modifications are needed?
- 6) What other social determinants should be considered in making treatment adaptations?

**Data Management and Analytic Plan** Recorded groups will be transcribed, and text data will be entered into NVivo, coded by two independent raters. We will use inductive coding methods based on pragmatic-variant grounded theory, to develop a coding tree based on both the focus group question framework and new themes identified in the focus group transcripts. We will use NVivo software for coding and analysis to identify prevalent themes. Pre-coding data exploration using the Word Frequency function will identify the most commonly-used words by focus-group. Commonly occurring words and phrases will be explored for meaning and context using the Word Tree function to create “meaning units.” Content will be further searched using “meaning units” to identify additional text representing relevant themes and. Repeated themes will be identified and coded as “nodes.” Links between themes and subthemes within each node will be explored using line-by-line coding.

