## **AIM 2**

*Aim 2* will involve adaptation of the iOTA intervention using the Stirman adaptation framework, including modification of contextual, content and training aspects of the treatment based on qualitative data collected using the I-Corps methods. These might include adaptations to the treatment manual, in-person visit structure, and SMS text messaging. Once adaptations have been completed, they will be tested for feasibility by members of the focus groups queried in Aim 1 via semi-structured interview. Final adaptations will be made based on interview data.

**Study Participants** Individuals who participated in Aim 1 focus groups will be queried with individual semi-structured interviews to obtain feedback on treatment adaptations.

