***Study Participants*** Aim 3 will include a randomized 24-week pilot study of the adapted intervention, followed by 12 weeks of text messaging intervention alone in 60 participants (30 at each study site). Participants will be CMHC clients aged 18-45 with eSMI receiving mental health services at each clinical site, and will be randomized 2:1, iOTA-eSMI intervention: health education control. Groups will be balanced to reflect the age, gender, racial and ethnic distribution of the client-base at each site. Targeted group size for this pilot study will permit exploration of treatment group interactions with age and with racial/ethnic differences. The study manager, under the supervision of the study statistician, will maintain control of the randomization matrix to ensure unbiased group assignment during the randomization process. Although this is not a blinded study, the PI's and health coaches will not be involved in any part of the randomization to further ensure an unbiased process.

***Inclusion criteria:*** i) aged 18-45 years, ii) "at-risk" weight defined as  $>7\%$  weight gain in the prior 2 years, overweight (BMI 25-29.9) OR class I obesity (BMI 30-32.49) iii) SMI diagnosis with  $<5$  years treatment,

iv) receiving case management services in one of the two CMHC study sites v) University of California, San Diego Brief Assessment of Capacity to Consent (UBACC) score  $> 14$  vi) not taking weight loss medications or participating in another behavioral weight loss intervention, vii) mild to moderate psychiatric symptom severity as measured by the Clinical Global Impression – Severity scale viii) willing and able to provide written informed consent.

**Exclusion criteria:** i) taking weight loss medications or participating in another behavioral weight loss intervention, ii) documented diagnosis of diabetes and/or treatment with an antidiabetes agent (diagnoses of hypertension and hyperlipidemia acceptable), iii) UBACC score  $\leq 14$ , iv) acute suicidality at time of screening, v) unwilling or unable to provide written informed consent.

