**Health Education Control:** A control condition that matches for group setting, time, and attention is necessary to minimize the chance that study findings might be attributable to non-specific differences in conditions rather than the active ingredients of the adapted iOTA intervention. Health Education is based on the Stanford health care self-management program developed by Kate Lorig and colleagues. Health Education improves chronic disease management, but it does not teach self-efficacy or psychophysical awareness, and does not involve specific empirically supported psychotherapeutic techniques to help with weight management. It matches iOTA in time and number of sessions. Participants randomized to the control condition will receive monthly in-person health coaching visits and a weekly SMS general "Health Tip" message. Visits will be structured according to current US Preventive Services Task Force recommendations to counsel participants on energy balance, physical activity and nutrition. The Health Coach will use educational materials developed for the iOTA-SMI adaptation for health education groups, which includes information from [www.MyPlate.gov](http://www.MyPlate.gov) and from the Be Fit Be Well program. Health education control group participants will not be engaged in formal goal setting.

**Ensuring Rigor & Reproducibility:** Behavioral intervention treatment fidelity is determined by structured, direct observation of individuals carrying out the behavioral intervention, evaluating for evidence of 1) adherence to the treatment protocol and 2) competence in the treatment delivery. The demonstration of treatment fidelity is critical to the development of a valid behavioral intervention, such that the intervention cannot be tested for efficacy in a randomized clinical trial, nor can said intervention be considered evidence-based until this critical step is accomplished. Therefore, a primary goal of the proposed project is to demonstrate treatment fidelity of the iOTA and Health Education Control in-person health coaching visits. This will be accomplished by audio-recording monthly in-person sessions, which will be reviewed by the PIs and discussed during weekly study teleconferences. Health Coaches will self-monitor treatment fidelity at each visit using an established Treatment Fidelity and Competence Rating Scale.

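### Aim 3 neither excludes nor identifies clients who used iOTA in Aim 1 or reviewed or tested the adaptation in Aim 2, so the pilot's acceptability and engagement summaries may mix prior users with new ones

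*Protocol*

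**What the plan says.** **Aim 1 exposure.** Under Focus Group Makeup, Preparation & Topics, once members are identified, "they will be asked to participate in one in-person or phone visit to set up health goals and related text messages". The next sentence adds the texting: "They will then participate in 1-2 weeks of iOTA text messaging so as to facilitate optimal feedback on intervention adaptations". Clients are not exempted. The Aim 1 inclusion criteria state that "participants for CMHC clients will include individuals ages 18-45 with SMI"; they set no weight, diabetes or treatment-duration limit.

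**Aim 2 review.** Once the adaptations are made, "they will be tested for feasibility by members of the focus groups queried in Aim 1 via semi-structured interview". The key informant procedures limit this to one or two members per group at each site. Separately, the iOTA adaptation procedures test the message libraries for usability in patients with early serious mental illness. The number of testers is not given.

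**Aim 3 eligibility.** Participants are clients aged 18 to 45 at the two study sites. The nearest exclusion is "taking weight loss medications or participating in another behavioral weight loss intervention", which describes what a person is doing now. The sections on recruitment and screening, randomisation and data analysis, and the SAP, do not mention prior iOTA exposure or Aim 1 or 2 participation.

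**Intended contrast.** On the control arm, the Protocol says: "Health education control group participants will not be engaged in formal goal setting".

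**Size of Aim 1.** The opening of Procedures plans "eight focus groups of five participants each, conducted at each CMHC site, for a total of 16 focus groups". Table 1 lists two client groups per site, with two or three clients each. The text after Table 1 says "Six focus groups will be conducted at each community site" and lists one client group.

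**The concern.** The SAP puts hypothesis testing and effect-size estimation outside the scope of this grant. What the pilot has to deliver is a fair picture of feasibility, tolerability, acceptability and target engagement for planning a larger trial. A client who volunteered for the design work, has already set goals with the team and has already used the texting system is not a typical clinic client. Such a person may answer texts, stay in the study, or rate credibility and acceptability differently from someone meeting iOTA for the first time. Without a marker in the dataset, nobody could later separate the two groups.

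There is a second, smaller issue. A former Aim 1 client randomised to control would already have had the goal setting that the control condition is designed to leave out. Case managers are in a similar position: they sit in Aim 1 groups and can later give staff ratings in Aim 3.

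**Working it through.** **1. The plan's own count.** Table 1 groups per site: 1+1+1+1+2+2 = 8. Two sites give 16 groups, and at five each 80 people, which matches the opening of Procedures. The later text gives 6 × 2 = 12 groups.

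**2. Clients exposed in Aim 1** (client groups per site × clients per group × 2 sites).
- Table 1 as printed: 2 × 2 × 2 = 8 to 2 × 3 × 2 = 12.
- One client group per site at the general size of five: 1 × 5 × 2 = 10.
- Two client groups of five: 2 × 5 × 2 = 20.

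The range is therefore 8 to 20. Pairing the single-group list with Table 1's two or three per group would give 4 to 6. I do not carry that forward, because those sizes belong to Table 1's two-group layout.

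**3. Clients interviewed in Aim 2.** At one or two per group: 1 × 1 × 2 = 2 (one client group per site) up to 2 × 2 × 2 = 8 (two groups). Message testers are extra and uncounted.

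**4. Carry-over into Aim 3.** With 60 participants at 2:1, the arms are 40 and 20. Let k be the number of prior participants enrolled. The expected number in control is k × 20/60 = k/3, and the chance of at least one exposed control is 1 − C(40,k)/C(60,k), treating allocation as a simple draw of 20 from 60. The fraction that both qualifies and enrols is my assumption.

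| Aim 1 pool | Fraction enrolling | k | Share of 60 | Expected exposed controls | Chance of at least one |
|---|---|---|---|---|---|
| 8 | 1/4 | 2 | 3.3% | 0.7 | 56% |
| 8 | 1/2 | 4 | 6.7% | 1.3 | 81% |
| 12 | 1/4 | 3 | 5.0% | 1.0 | 71% |
| 12 | 1/2 | 6 | 10.0% | 2.0 | 92% |
| 20 | 1/4 | 5 | 8.3% | 1.7 | 88% |
| 20 | 1/2 | 10 | 16.7% | 3.3 | 99% |

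A pool of 10 lies within these rows. The ceiling, if every Aim 1 client enrolled, is 8/60 = 13% to 20/60 = 33%.

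**5. Effect on an acceptability proportion.** With naive rate p, prior-participant rate q and share s, the observed rate is p + s(q − p). The documents give neither p nor q. For illustration, take p = 70% and q = 90%:
- s = 3.3%: 70.7%
- s = 16.7%: 73.3%
- s = 33.3% (ceiling): 76.7%

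If prior participants were instead more critical, say q = 50%, then s = 16.7% gives 70 − 3.3 = 66.7%.

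**6. Effect on the weight contrast.** If exposed controls retain a fraction c of the intervention effect, the observed contrast is 1 − s × c of the true one. For c between 10% and 50% (assumed):
- s = 3.3%: 99.7% to 98.3%
- s = 16.7%: 98.3% to 91.7%
- s = 33.3% (ceiling): 96.7% to 83.3%

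**The case against.** The strongest reply is that overlap is possible but not planned. The recruitment section relies on fliers, provider referral and record review, and nowhere says that Aim 1 clients will be approached. The overlap is documented only at the level of the two centre systems; the Aim 1 clinics are not named. Aim 3 also applies limits that Aim 1 does not: at-risk weight, under five years of treatment, no diabetes, a capacity score and a symptom-severity range. Many Aim 1 clients may not qualify. This stands, and it makes 20 of 60 an unlikely ceiling. It does not close the gap, because those who do qualify would enter unmarked, and the Aim 2 message testers are drawn from the early-illness population itself.

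Second, the exposure is short: one visit and one or two weeks of texts before adaptation, against 24 weeks of intervention. Everyone in Aim 3 has a week of test messaging before randomisation, and weight change is measured from a baseline taken after any Aim 1 exposure. This largely disposes of the weight contrast. The run-in does not equalise the arms' history fully, since its stated purpose is to check that texts can be received and answered, and no goal setting is described.

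Third, the direction is unknown. Aim 1 deliberately seeks outlying views, and such people may rate the programme lower. Baseline credibility and expectation are also measured, so part of this pathway is visible. Both points stand.

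A reader might infer that the acceptability results will be inflated, that the control arm is contaminated, or that the plan contradicts its own description of control. The documents do not support any of these. They contain no data on how prior participants rate, and the control description concerns what is delivered during the trial. Nor should every Aim 1 client be treated as a co-designer, since only about 2 to 8 are interviewed in Aim 2.

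**Conclusion.** The gap is real and modest. As written, the plan allows prior iOTA users, and a few people who reviewed or tested the adaptation, to enter Aim 3 without being identified. On the assumption that a quarter to a half of the 8 to 20 exposed clients qualify and enrol, they would make up 3% to 17% of the sample, with roughly one to three of them in control. What is at stake is how well the feasibility summaries describe a new client; the size and sign of any distortion cannot be worked out from the documents. Dilution of the weight comparison is probably minor. The change is worth making because these summaries are the pilot's main product and the problem cannot be repaired afterwards unless prior participation is recorded.

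**What to change.** Add one line to the Aim 3 exclusion criteria: participated as a client in Aim 1 or Aim 2. That wording also covers the message testers. The documents do not support extending it to earlier iOTA studies: the prior pilot was in chronic illness, which the under-five-years criterion should largely keep out.

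Where these clients are needed to reach 60, or some are already randomised, record prior Aim 1 or 2 participation in REDCap at screening. Report the feasibility (including retention), acceptability, expectation and text-response summaries with and without them, by arm. Optionally, flag staff raters who took part in Aims 1 or 2 and show staff ratings both ways.

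Reconcile the Aim 1 group counts and client numbers at the same time, since they fix the size of the exposed pool.

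Cost: under exclusion, at most 8 to 20 Aim 1 clients plus any message testers are lost as recruits, and the target stays at 60 (40 and 20). Under the alternative, the cost is one database field and a repeated set of summaries.
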